## **2.g Early Withdrawal of Subjects**

- The participants may withdraw by telling the study team they are no longer interested in participating in the study or by sending in a withdrawal letter.
- The investigator might end a subject's participation in this research study earlier than planned. This may happen for no reason, because in the treating physician or study team's judgment it would not be beneficial for the participant to continue, because the participant's condition has become worse, or because the research has ended.

## 2.h When and How to Withdraw Subjects

Subjects can be withdrawn from the study at any time by communicating directly to the study team or sending a withdrawal letter.

## 2.i Data Collection and Follow-up for Withdrawn Subjects

All data collection and follow-up for the purposes of the study will be terminated for subjects withdrawn from the study. At the time of withdrawal, if the participant is clinically doing well and the programmed CRT settings are deemed clinically appropriate they will be retained, else the CRT programming may be changed as per standard of care.

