# **C Study Objectives**

## **C1 Specific Aim**

**To determine the impact of individualized RV-LV pacing offset to optimize ECG on reverse cardiac remodeling and other heart failure surrogate endpoints:**

After CRT implant, we will *randomize* patients to either (A) active intervention of programming individualized RV-LV offset to optimize ECG or to (B) active control of nominally programming CRT device without RV-LV pacing offset. The *primary outcome* will be the reverse cardiac remodeling after 3-12 months, as assessed by LV end-systolic volume on echocardiography. The secondary outcomes will include quality-of-life (Kansas City Cardiomyopathy Questionnaire-12, KCCQ-12), functional performance (6-minute hall walk distance) and a prognostic biomarker (serum NT-proBNP).

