**Treatment and control arms:** All study patients will receive standard of care clinically indicated medical and device therapy per their treating physicians. After implant of a clinically indicated CRT device or upgrade of a preexisting pacemaker or defibrillator device to CRT system, participants will be randomized 1:1 to treatment arms (A) active intervention of programming individualized RV-LV pacing offset to optimize ECG or to (B) active control of nominally programming CRT device without RV-LV offset. Of note, both intervention and control treatment are active FDA-approved CRT therapies and no investigational device or programming will be used, and no clinically indicated treatment will be withheld from any patient. At any time, if in the judgment of the patient's treating physicians or the research team, any treatment including CRT programming different from the study protocol is necessitated for clinical reasons, the appropriate clinically indicated changes will be made. At the end of the study, if the participant is clinically doing well and the programmed CRT settings are deemed clinically appropriate they will be retained, else the CRT programming may be changed as per standard of care.

Enrolled participants who have a failed or unsatisfactory LV lead implant will not be randomized.

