## **2.e Randomization Method and Blinding**

A 1:1 randomization scheme using a random allocation table in REDCap will be used. The patient and personnel assessing study outcomes will be blinded to the randomized assignment.

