## **F Statistical Plan**

### **F1 Sample Size Determination and Power**

We plan to randomize 200 patients that may require enrollment of up to **250 patients**. This gives us 80% power to detect a between-treatment difference of  $\geq 2 \pm 5\%$  in the % reduction in LV end-systolic volume from baseline with a 2-sided  $\alpha$ -error 0.05. Previous studies have shown that a reduction in LV end-systolic volume from baseline is associated with an improvement in clinical outcomes. As both the study and control arms will receive CRT, albeit with different approach to programming RV-LV offset, any statistical difference in reverse cardiac remodeling between the two RV-LV offset programming strategies will be clinically important.

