### **F2 Statistical Methods**

The primary outcome of interest is the LV end-systolic volume. Secondary outcomes include quality-of-life (KCCQ-12), functional performance (6-minute hall walk distance) and a prognostic biomarker (serum NT-proBNP). We will perform **t-tests** to assess for differences in the % change from baseline in primary and secondary endpoints between treatment groups. Sub-analyses will evaluate for effect modification by subgroups based on ischemic vs. non-ischemic cardiomyopathy, sex, and magnitude of RV-LV offset based on ECG. We prespecify evaluation of the subgroup with ECG optimized RV-LV offset  $\geq 40$  msec. A two-tailed p-value 0.05 will be considered as threshold for statistical significance.

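### Section 2.i ends all data collection even when the investigator, not the patient, ends participation, so a primary echo that could be obtained can be lost for a reason related to poor response

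*Combined protocol and SAP*

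**What the plan says.** Section 2.g, under a heading on early withdrawal, covers two routes out of the study. The participant may leave, or the investigator may end participation. The grounds listed for the investigator finish with the participant's "condition has become worse, or because the research has ended".

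Section 2.h describes only the communication route: "Subjects can be withdrawn from the study at any time by communicating directly to the study team or sending a withdrawal letter".

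Section 2.i applies one rule to everyone described as withdrawn: "All data collection and follow-up for the purposes of the study will be terminated for subjects withdrawn from the study".

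The primary outcome in C1 "will be the reverse cardiac remodeling after 3-12 months, as assessed by LV end-systolic volume on echocardiography". F2 uses t-tests "to assess for differences in the % change from baseline in primary and secondary endpoints between treatment groups". F1 and F2 name no analysis population, no method for missing outcomes, no sensitivity analysis and no allowance for loss after randomisation.

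Two other provisions bear on the point. D1 allows departures from the assigned programming during the study: if "any treatment including CRT programming different from the study protocol is necessitated for clinical reasons, the appropriate clinically indicated changes will be made". Section 2.e says "The patient and personnel assessing study outcomes will be blinded to the randomized assignment".

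**The concern.** The endpoint measures how far the ventricle has remodelled. A patient who is deteriorating is plausibly one whose LV end-systolic volume (LVESV) has not improved. If the investigator ends participation on that ground before the follow-up echo, 2.i tells staff not to obtain it, even when the patient would attend. The patient then has no percentage change from baseline and cannot enter the t-test. Missingness of this kind can depend on the value that is missing, and a comparison of completers does not correct for it.

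Loss could also differ between arms. Section 2.e blinds the patient and the outcome assessors, but the people who decide to end participation are not stated to be blinded. This is a possibility that the text leaves open; the documents do not show that it happens.

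The target difference is only 2 percentage points, so a bias of a few tenths of a point would matter.

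**Working it through.** **Reading the sections together.** 2.g puts both routes under one withdrawal heading, and 2.i refers to withdrawn subjects without distinguishing them. The extended chart review (D1, E2) and adverse event tracking (E3) supply no echo. Withdrawal after the follow-up echo loses no primary data, so the exposure is limited to withdrawal before it.

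**The plan's own figure.** Inputs from F1 and 2.e: difference 2, the 5 read as the SD, two-sided alpha 0.05, power 80%, 1:1 allocation; "We plan to randomize 200 patients that may require enrollment of up to" 250.
- Normal approximation: n per arm = 2 × (1.960 + 0.842)² × 5² / 2² = 98.1, so 99 per arm or 198 in total.
- Exact t-test: 99.08, so 100 per arm or 200 in total. The stated size is reproduced.

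**Room for loss (noncentral t, random loss).**

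| Evaluable per arm | Power |
|---|---|
| 100 / 100 | 80.36% |
| 100 / 99 | 80.17% |
| 99 / 99 | 79.97% |
| 95 / 95 | 78.3% |
| 90 / 90 | 76.1% |

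The second loss takes power just below 80%. Each patient costs only about 0.2 points, so the crossing itself has little practical meaning; it shows that no reserve was built in. The margin from 200 to 250 lies between randomised and enrolled patients. D1 gives one reason for it: patients with a failed or unsatisfactory LV lead are not randomised.

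**Outcome-related loss: assumptions.** The outcome is normal with SD 5. Withdrawal occurs below a threshold on a latent score that correlates ρ with percentage LVESV reduction. Loss rates of 5-15% and both values of ρ are assumed. With a fraction p lost, the retained mean shifts by ρ × 5 × φ(z_p) / (1 − p). At ρ = 1:
- p = 5%: 5 × 0.1031 / 0.95 = 0.543
- p = 10%: 5 × 0.1755 / 0.90 = 0.975
- p = 15%: 5 × 0.2332 / 0.85 = 1.372

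At ρ = 0.5 each shift is halved.

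**No true difference, unequal loss.** Bias is the difference between the two shifts.

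| Loss by arm | Bias, ρ = 0.5 | Two-sided error | Bias, ρ = 1 | Two-sided error |
|---|---|---|---|---|
| 5% / 10% | 0.22 | 6% | 0.975 − 0.543 = 0.43 (22% of target) | 10% |
| 5% / 15% | 0.41 | 9% | 1.372 − 0.543 = 0.83 (41% of target) | 25% |

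Equal loss with equal selection gives zero bias. A simulation of 20,000 trials at ρ = 1 gave bias 0.435 and 0.823, and error 10.0% and 24.7%.

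**True 2-point benefit, one worsening threshold in both arms.** The intervention arm then loses fewer patients.

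| Control loss | Intervention loss, ρ = 0.5 | Observed difference | Power | Power, same numbers lost at random |
|---|---|---|---|---|
| 5% | 3.3% | 1.92 | 77% | 78.7% |
| 10% | 6.9% | 1.87 | 74% | 76.8% |
| 15% | 10.8% | 1.84 | 71% | 74.7% |

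At ρ = 0.5 selection accounts for about 2 to 4 points of the power drop; half or more of the drop is simply fewer patients. The extreme ρ = 1 gives observed differences of 1.71, 1.53 and 1.40, with power of about 73%, 66% and 60%.

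**The case against.** The strongest case against is that the size is assumed throughout. No rate, mix of reasons or imbalance between arms is documented, and the largest figures need both perfect selection and a threefold difference in loss. The model also charges all loss to 2.i. Patients who die, are too ill to attend or withdraw consent have no echo whatever 2.i says. Only those whose participation the investigator ends, and who could still attend, are recoverable. Both criticisms stand, so the figures are illustrations and upper limits.

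There are real mitigations. D1 lets a worsening patient be reprogrammed and stay in the study. The 3-12 month window may allow the echo before participation ends. Patients and assessors are blinded. The exclusion criteria remove those unable to comply with follow-up or with life expectancy of one year or less. These reduce the risk, but none requires that the echo be obtained.

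It can be argued that 2.i was meant only for the route in 2.h. The heading of 2.g and the undivided wording of 2.i favour the wider reading. If the narrow one is intended, 2.i should say so.

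A reader might also infer more than the text supports:
- That worsening obliges withdrawal. 2.g only permits it.
- That the result will favour one arm. More such losses in an arm make that arm look better than it is, while a common threshold with a true benefit shrinks the observed effect; the direction is unknown.
- That data already obtained are discarded. 2.i ends collection and does not say this.
- That 2.i contradicts adverse event tracking in E3. That tracking is tied to study participation, so the conflict is weak.

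**Conclusion.** The point holds in a limited form. The plan contains a rule, not merely a missing detail, under which a patient who is willing and able to attend can lose the primary outcome because the investigator ended participation for worsening. Nothing elsewhere restores the echo or handles its absence in the analysis.

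How often this would happen is unknown, as are the size and direction of any bias. Under the assumed 5% against 10% loss, a moderate link with outcome gives about a tenth of the target difference (0.22 / 2 = 11%) and perfect selection about a fifth. Only part of that is recoverable by rewording. The power argument is secondary: 80.4% at full numbers, 79.97% at 99 per arm. All of this takes the 5 in F1 as the SD and a normal outcome. The change is worth making because it is cheap and an echo not done cannot be recovered later.

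**What to change.** - **Section 2.i:** stop data collection only when the patient withdraws consent. When the investigator ends participation, still seek the scheduled follow-up echo, the other outcomes and chart review where the patient consents and is able.
- **F2, population:** analyse all randomised patients with outcome data in their assigned arm.
- **F2, missing LVESV:** add a prespecified sensitivity analysis for values that remain missing, with an arm-specific delta adjustment over a range stated in advance. It is needed even after the change to 2.i, because some patients will be too ill or unwilling to attend.

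The cost is protocol and consent wording with ethics review of follow-up after investigator-ended participation, a few visits already in the study calendar, and modest analysis work. The change concerns data collection and analysis only; it proposes nothing about when treatment or participation may be ended.

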# E Study Procedures

## E1 Screening for Eligibility

Patients for this study will be screened and approached for participation prior to or after a clinical CRT implant/upgrade procedure at Barnes-Jewish Hospital Clinical.

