## **A Introduction**

### **A1 Study Abstract**

Heart failure with reduced ejection fraction is a major global health problem. Every year, over 200,000 patients with heart failure receive pacing device implants for cardiac resynchronization therapy (CRT). However, one-third of the patients receiving CRT do not derive any benefit, a large population with refractory heart failure symptoms, high mortality, and tremendous healthcare costs. Our overall objective is to reduce heart failure by physiological individualized optimization of CRT pacing therapy guided by 12-lead electrocardiography (ECG).

Patients with heart failure and left bundle branch block benefit from CRT. This delivers pacing from right ventricle (RV) and left ventricle (LV) synchronously, the resultant ventricular electrical resynchrony leading to improved cardiac mechanics and acute hemodynamics, and subsequent reverse structural cardiac remodeling. This leads to reduced heart failure symptoms, hospitalizations and death. It is not known if programming an individually optimized RV-LV pacing offset to maximize electrical resynchrony can improve benefit from CRT.

The proposed study is a *randomized controlled trial* in patients undergoing implant of a CRT pacemaker/defibrillator device for clinical indications to evaluate benefit of RV-LV offset programming using ECG vs. standard nominal CRT programming without RV-LV offset. Patients receiving CRT devices will be randomized to either (A) active intervention of programming individualized RV-LV pacing offset to optimize ECG or to (B) active control of nominally programming CRT device without RV-LV offset. The patients will be followed to evaluate changes in heart failure endpoints including echocardiography, quality-of-life, functional performance and a blood biomarker.

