## **D2 Subject Selection and Withdrawal**

### **2.a Inclusion Criteria**

1. Patients  $\geq 18$  years of age who are able to give consent.
2. Diagnosis of systolic heart failure.
3. Planned to undergo new CRT device implant (or upgrade of preexisting pacemaker or defibrillator device to CRT system) for standard clinical indications.
4. Expected to have over 95% heart beats resynchronized with CRT (absence of competing arrhythmias or plans to not immediately activate CRT therapy).

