## E2 Schedule of Measurements

The baseline evaluation will encompass one, two or more visits in the time window 6 weeks prior to 2 weeks after CRT device implant/upgrade date. If the patient passes the eligibility screening and signs informed consent, their baseline evaluation will include echocardiogram, quality-of-life questionnaire, 6-minute hall walk, blood test, vital signs, ECGs, device interrogation and baseline demographic and medical history including chart review. After CRT device implant, participants will undergo physiologic evaluations at various (up to 10 or more) RV-LV offset settings including ECGs and echocardiography. The randomized CRT pacing assignment will be programmed.

The follow-up evaluation (usually 3-12 months) will encompass one or more visits and include echocardiography, quality-of-life questionnaire, 6-minute hall walk test, blood test, vital signs, ECGs, device interrogation, and follow-up medical history including chart review. The patients will continue to be in extended follow-up through review of their medical charts till the end of the study (12 months from date of CRT implant/upgrade of the the last study participant).

Table 2.  

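### Baseline measurements may be taken before CRT in some patients and with CRT running in others, and the analysis of % change does not allow for it

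*Combined protocol and SAP*

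**What the plan says.** - **Approach (E1).** Patients may be "screened and approached for participation prior to or after a clinical CRT implant/upgrade procedure". E2 places the baseline evaluation after consent, so a patient approached after implant has a post-implant study baseline.
- **Baseline window (E2).** The evaluation may take one or several visits "in the time window 6 weeks prior to 2 weeks after CRT device implant/upgrade date". D1 and Table 2 give the same window, so this is not a slip in one sentence.
- **Eligibility (2.a).** Criterion 3 admits patients "Planned to undergo new CRT device implant" or an upgrade. Criterion 4 expects more than 95% of beats to be resynchronized, explained as "absence of competing arrhythmias or plans to not immediately activate CRT therapy".
- **Mechanism (A1).** Resynchrony is said to lead to "improved cardiac mechanics and acute hemodynamics, and subsequent reverse structural cardiac remodeling".
- **Endpoint and power (F1).** "We plan to randomize 200 patients that may require enrollment of up to" 250. The power statement concerns the "reduction in LV end-systolic volume from baseline", in percent.
- **Analysis (F2).** t-tests compare % change from baseline between arms, for the primary and the secondary outcomes. Section 2.e describes randomization only as 1:1 from an allocation table.

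No section fixes the pacing state for the baseline echo, or stratifies or adjusts for it.

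**The concern.** Baseline is both the reference and the denominator of the primary endpoint. A pre-implant baseline captures everything that happens after CRT begins. A baseline taken on CRT leaves out whatever change CRT has already produced by then. The planned t-test pools the two as one quantity.

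The same holds for the secondary outcomes, which F2 also analyses as % change. A late KCCQ-12, walk or NT-proBNP additionally falls within two weeks of a device procedure. Because baseline may span several visits, one patient's measurements can also be in different states.

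At stake are precision and a clear meaning for the per-arm mean % reduction. F1 has almost no spare power, so added between-patient variance is paid for directly. Requiring baseline to precede programming of the assigned setting is a separate matter. It would not settle this one, because CRT may already be running when that programming is done.

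E1 and inclusion criterion 3 also need reconciling: a patient approached after the procedure is no longer planned to undergo it.

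**Working it through.** **Inputs from the plan.** 200 randomized 1:1 (100 per arm); two-sided alpha 0.05; difference 2 points and SD 5 points, reading F1's 2 ± 5% as difference ± SD.

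**The plan's own figure.** A two-sample t-test with standardized difference 2/5 = 0.4 needs 99.1 per arm for 80% power. At 100 per arm the power is 80.4%. F1 reproduces.

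**Assumptions not in the documents.**
- q: share of patients with a CRT-on baseline.
- a: shift in % reduction, in points, between the two baseline states.
- The SD of 5 holds within each state.

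**Formula.** Ignoring baseline state, the variance is 25 + q(1 − q)a², so SD = √(25 + q(1 − q)a²). Example with a = 5 and q = 0.25: 0.25 × 0.75 × 25 = 4.69; SD = √29.69 = 5.45; power 73.3%.

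SD and power at 100 per arm, difference 2:

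| | q = 5% | q = 10% | q = 25% | q = 50% |
|---|---|---|---|---|
| a = 3 | 5.04; 79.7% | 5.08; 79.1% | 5.17; 77.8% | 5.22; 76.9% |
| a = 5 | 5.12; 78.5% | 5.22; 76.9% | 5.45; 73.3% | 5.59; 71.1% |
| a = 10 | 5.45; 73.2% | 5.83; 67.5% | 6.61; 56.7% | 7.07; 51.2% |

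**Chance imbalance is the same cost.** Under simple randomization, imbalance in baseline state contributes a standard error of a√(2q(1 − q)/100) to the difference. At a = 5 and q = 0.25 this is 0.306. Without the mixture the standard error is 5√(2/100) = 0.707. Combined: √(0.707² + 0.306²) = 0.771, which equals 5.45√(2/100). Imbalance is how the added variance reaches the estimate, and it must not be counted again.

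**Which remedy recovers the power (simulation, same assumptions).** Stratifying the randomization by baseline state but keeping the unadjusted t-test moves power from 71% to 73% (a = 5, q = 50%) and leaves it at 51% (a = 10, q = 50%). Including baseline state in the analysis model brings power back to 79–81%.

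**The case against.** Several objections have force.

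- **The documents permit mixing; they do not say it will happen.** The late window may be meant for items such as device interrogation, which cannot be done before a first implant. That is possible, but no section restricts it so. The point has to be put as what may happen.
- **Criterion 4 is an expectation at eligibility.** A reader might infer that it requires immediate activation and so proves that every post-implant baseline is on CRT. It only rules out planned delay and does not set the pacing state during the echo.
- **No acute LVESV change is documented.** A1 separates acute mechanics and hemodynamics from later remodelling, and C1 treats LVESV as the remodelling measure. The shift a is therefore an inference, and a small a or q makes the loss trivial: 79.7% power at a = 3, q = 5%.
- **The SD of 5 has no stated source.** It may already include some mixing, in which case the loss is smaller.
- **Pacing state may be partly recoverable.** ECGs and device interrogation are part of baseline. What is missing is a link in time to the echo, and use in the analysis.
- **Randomization protects the comparison.** If baseline precedes programming, its state is balanced between arms in expectation. This stands, and it limits the harm to variance and clarity.

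None of this removes the gap. The window, the approach rule and the unadjusted analysis together allow the mixture and ignore it.

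**Conclusion.** The concern holds as one of precision and definition. Followed as written, the plan can mix pre-CRT and CRT-on baselines in one % change endpoint with nothing in the analysis to separate them. Power falls from 80.4% to about 77–80% (a = 3), 71–79% (a = 5) or 51–73% (a = 10) for q between 5% and 50%. These ranges rest on assumed a and q, and on the SD of 5 excluding the mixture. The lowest values need both a = 10 and q of at least 25%.

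A reader might go further and call the result biased or uninterpretable. The documents do not support that where baseline precedes programming: the difference between arms remains a fair comparison, made with more noise. It is the per-arm mean reduction that loses a clear meaning. Nor is chance imbalance in baseline state a second harm on top of the power loss.

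**What to change.** 1. In E1, E2 and Table 2, define the baseline echo for the primary outcome as the pre-implant one. For a patient approached after implant, use an existing clinical echo from the 6-week pre-implant window, read by the blinded reader. Chart review is already part of baseline.
2. Reconcile E1 with inclusion criterion 3.
3. Where only a post-implant baseline exists, keep the patient. Record pacing state and timing relative to implant at the baseline visit, when this is easiest to establish.
4. In F2, include baseline state (pre-implant or CRT-on) as a factor in the primary and secondary analyses. Define it separately for each outcome, since a patient may have a pre-implant echo but a post-implant walk, KCCQ-12 or NT-proBNP.
5. Optionally, also use baseline state as a randomization stratum. Stratifying without adjusting recovers little.

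The cost is a few baseline echoes of clinical rather than research quality, the recording of state and timing, and one extra model term. No exclusion rule is needed. The gap between 200 randomized and 250 enrolled should not be treated as room for one: F1 says only that up to 250 may be required, and D1 gives failed or unsatisfactory LV leads as a reason for not randomizing. One limit remains: upgrade patients already have a device, so even pre-implant baselines may include native and RV-paced states, which is a further reason to record the state.
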